#### **6.7.7. Survival, Transformation to Acute Myeloid Leukemia (only for Myelodysplastic Syndromes Cohort Subjects), and Subsequent Myelodysplastic Syndromes/Acute Myeloid Leukemia Therapies**

All subjects discontinued from protocol-prescribed therapy for any reason should undergo treatment discontinuation procedures (Section 6.14) and be followed for survival, disease transformation to AML, and subsequent MDS/AML therapies (Section 6.15). Data regarding subsequent therapies, determination of disease progression, and date and cause of death will be recorded in the appropriate eCRF and in the subject's source documents.

CCI [REDACTED]

[REDACTED]

[REDACTED]

- [REDACTED]
- [REDACTED]
- [REDACTED]
- [REDACTED]
- [REDACTED]
- [REDACTED]
- [REDACTED]
- [REDACTED]
- [REDACTED]
- [REDACTED]
- [REDACTED]
- [REDACTED]
- [REDACTED]
- [REDACTED]
- [REDACTED]
- [REDACTED]
- [REDACTED]
- [REDACTED]
- [REDACTED]

[REDACTED]

[REDACTED]

- [REDACTED]
- [REDACTED]
- [REDACTED]
- [REDACTED]

CCI [REDACTED]

[REDACTED]

[REDACTED]

### 6.9. Pharmacokinetics

All subjects receiving the combination therapy will participate in the PK procedures.

#### Durvalumab PK sample collection:

Blood samples for durvalumab PK analysis will be collected, processed, and analyzed. Samples will be collected at the following timepoints:

- Cycle 1 Day 1: end of infusion (EOI).
- Cycle 2 Day 1: preinfusion (-90 to -5 minutes prior to dose).
- Cycle 4 Day 1: preinfusion (-90 to -5 minutes prior to dose) and end of infusion.
- Cycle 6 Day 1: preinfusion (-90 to -5 minutes prior to dose).
- Safety Follow-up Visit (90 days after the last dose of durvalumab) .

CCI [REDACTED]

[REDACTED]

[REDACTED]

[REDACTED]

[REDACTED]

[REDACTED]

[REDACTED]

[REDACTED]

[REDACTED]

[REDACTED]

CCI

### 6.13. Unscheduled Visits

Should it become necessary to repeat an evaluation (eg, laboratory tests, vital signs, etc) outside of scheduled study visits, the results of the repeat evaluation should be recorded in an unscheduled visit eCRF. These evaluations should also appear in the subject's chart and/or other source documentation.

### 6.14. Discontinuation from Study Treatment

Prior to discontinuing a subject from study treatment, it is recommended that the Investigator contact the sponsor's medical monitor and forward appropriate supporting documents for review and discussion. The decision to discontinue a subject remains the responsibility of the treating physician and will not be delayed or refused by the sponsor.

All subjects who have received at least one dose of IP should undergo the Treatment Discontinuation Visit within 7 days of the treatment discontinuation, where the following procedures will be performed: including:

- AEs including AESI
- Physical examination
- Vital signs
- Body weight
- ECOG performance status
- Electrocardiogram
- Hematology
- Serum chemistry (to include amylase and lipase)
- Thyroid function tests
- Urinalysis
- Pregnancy test (FCBP only)
- Concomitant medications, therapies and procedures

- Transfusion assessment
- Bone marrow aspirate/biopsy and peripheral blood smear
- CCI
- Cytogenetics
- IWG response assessment
- General disease status assessment
- CCI
- CCI
- Disease transformation to AML (MDS subjects only)
- Subsequent MDS/AML therapies (following IP discontinuation, if applicable).

If a subject is discontinued during a regularly scheduled visit, all treatment discontinuation procedures should be completed at that visit. If a procedure had been performed within 7 days of the Treatment Discontinuation Visit, it does not need to be repeated.

The reason for discontinuation will be recorded on the eCRF and in source documents for all randomized subjects.

In the event that a subject assigned to the combination treatment arm discontinues treatment with durvalumab or subcutaneous azacitidine because of drug-related toxicity, treatment with single-agent durvalumab or subcutaneous azacitidine may continue until any discontinuation criterion is met.

### 6.15. Follow-up

All subjects discontinued from treatment with IP for any reason will be followed for a period of at least 28 days after the last dose of subcutaneous azacitidine and 90 days after the last dose of durvalumab or until the date of the treatment discontinuation visit, whichever is later. During Safety Follow-up Visits, the following assessments will be performed:

- AEs including AESIs (monitored until 28 days after last dose of subcutaneous azacitidine or 90 days after last dose of durvalumab)
- physical examination
- vital signs
- body weight
- ECOG performance status
- hematology
- serum chemistry (to include amylase and lipase)
- thyroid function tests
- pregnancy testing (FCBP only)

- urinalysis
- concomitant medications, therapies and procedures
- transfusion assessment
- subsequent MDS/AML therapies
- survival

Females of childbearing potential should avoid becoming pregnant for at least 90 days after the last dose of IP and male subjects should avoid fathering a child for at least 90 days after the last dose of IP. The ICF will address any country-specific requirements, as needed.

All subjects discontinued from protocol-prescribed therapy for any reason will also be contacted by telephone every 3 months (12 weeks  $\pm$  14 days) following the Safety Follow-up Visit(s) until the last active subject reaches 12 months of treatment, unless additional follow-up is needed to evaluate time-to-event endpoints (eg, PFS and survival), or until death, lost to follow-up, withdrawal of consent to further follow-up, or study closure to collect information related to:

- survival
- subsequent MDS/AML therapies
- disease transformation to AML (only for MDS cohort subjects).

The Investigator must make every effort to obtain information regarding the subject's follow-up status. All attempts to contact the subject must be documented and appropriate due diligence must be demonstrated before the subject can be considered lost to follow-up (eg, 3 unsuccessful attempts by telephone and one unanswered written attempt sent by certified or traceable post).

## 7. DESCRIPTION OF STUDY TREATMENTS

### 7.1. Description of Investigational Product(s)

#### 7.1.1. Durvalumab

Durvalumab will be supplied by Celgene in single-use vials in single-count cartons. Each 10 mL vial will be supplied as a vial liquid solution containing 500 mg (nominal) of durvalumab at a concentration of 50 mg/mL. Durvalumab is stored at 2°C to 8°C (36°F to 46°F) and must be used before the individually assigned expiry date on the label.

Site to supply the following:

- Intravenous infusion bags of normal saline (0.9% [w/v] sodium chloride injection, 250 mL size). Saline bags must be latex-free and can be made of polypropylene, polyethylene, polyolefin copolymers, or polyvinyl chloride. Infusion lines should contain a 0.2-µm in-line filter.
- Since the compatibility of durvalumab with other IV medications and solutions, other than normal saline is not known, the durvalumab solution must not be infused through an IV line in which other solutions or medications are being administered.

Refer to the current durvalumab IB for detailed information about the physical properties of durvalumab and to the pharmacy manual for additional preparation, administration, or storage information.

#### 7.1.2. Azacitidine

Azacitidine will be supplied by Celgene as a sterile lyophilized powder containing 100 mg of azacitidine and 100 mg of mannitol per vial. Each single-use vial will be supplied in single-count cartons.

Refer to the current azacitidine IB for detailed information about the physical properties of azacitidine and to the pharmacy manual for additional preparation, administration, or storage information.

### 7.2. Treatment Administration and Schedule

#### 7.2.1. Treatment Administration

Subjects will receive treatment in 28-day cycles as described in the section below and may continue to receive the protocol therapy for as long as they benefit from the treatment or until treatment is discontinued for reasons detailed in Section 6.14.

Investigational product administration will be accurately recorded including, but not limited to, date of administration, dose, and any changes in dose administration (eg, interruption or reduction in dose due to an AE). For additional information on preparation and storage please refer to the pharmacy manual.

### 7.2.1.1. Azacitidine Dispensation and Administration

Azacitidine will be administered on Days 1 to 7 of each treatment cycle. The subject may not receive IP for each treatment cycle until all Day 1 procedures have been completed.

Vials/syringes should be used for the specific subjects to whom they are assigned, and must not be shared between subjects.

For FCBP subjects, a pregnancy test must be performed, and a negative result verified by the Investigator, within 72 hours prior to IP administration on Day 1 of each treatment cycle.

Subjects will receive azacitidine 75 mg/m^2/day subcutaneous for 7 days (Days 1 to 7) every 28 days. In the event 2 or fewer doses are missed during the 7-day dosing period, dosing should continue so the subject receives the full 7 days of therapy. If 3 or more days are missed during the 7-day dosing period, the Investigator should contact the sponsor and a decision on dosing will be made on a case-by-case basis.

Subjects assigned to the combination treatment arm will have azacitidine administered on Day 1 of each treatment cycle approximately one hour after completion of the durvalumab infusion, after resolution of any related AE immediately after durvalumab infusion, if any.

If the dose of azacitidine is modified during the course of the study (Section 7.2.2.1) and benefit is demonstrated at a dose lower than 75 mg/m^2, that dose should be maintained during subsequent cycles that are given (unless toxicity develops).

### 7.2.1.2. Durvalumab Dispensation and Administration

Total in-use storage time from needle puncture of durvalumab vial to start of administration should not exceed 4 hours at room temperature or 24 hours at 2°C to 8°C (36°F to 46°F). If in-use storage time exceeds these limits, a new dose must be prepared from new vials. Durvalumab does not contain preservatives and any unused portion must be discarded.

Sites should follow standard and local aseptic procedures and instructions from the pharmacy manual for all activities. All dispensing activities should be documented according to local procedures. The shelf lives stated above are based on chemical and physical stability; assignment of microbial shelf life is the responsibility of the clinical center and should be aligned with local procedure for managing microbial risk as long as the times specified in this section are not exceeded. Vials should be used for the specific subjects to whom they are assigned, and must not be shared between subjects.

The preparation of infusion bags should be done under aseptic conditions by trained personnel; they should not be prepared on the ward.

Vials containing durvalumab may be gently inverted for mixing, but should not be shaken. All durvalumab vials should be equilibrated to room temperature for 30 minutes prior to dose preparation.

Subjects will receive durvalumab, 1500 mg intravenously on Day 1 of each 28-day treatment cycle by IV infusion over approximately 1 hour (± 5 minutes). Infusions of durvalumab may be interrupted, slowed, or discontinued in order to address toxicity, but dose reduction of durvalumab is not permitted (see Section 7.2.2.2).

Refer to the current durvalumab IB for detailed information about the physical properties of durvalumab and to the pharmacy manual for additional preparation, administration, or storage information.

### 7.2.1.3. Monitoring of Durvalumab Dose Administration

Subjects will be monitored during and after infusion of durvalumab. Vital signs will be measured within 30 minutes prior to durvalumab administration, every 15 minutes ( $\pm$  5 minutes) during durvalumab administration, at the end of the durvalumab infusion ( $\pm$  5 minutes), and at 30 minutes ( $\pm$  5 minutes) and 60 minutes ( $\pm$  5 minutes) postinfusion of durvalumab, followed by a 2-hour ( $\pm$  15 minutes) period of observation.

In the event of a  $\leq$  Grade 2 infusion-related reaction, the infusion rate of durvalumab may be decreased by 50% or interrupted until resolution of the event (up to 4 hours) and re-initiated at 50% of the initial rate until completion of the infusion. For subjects with a  $\leq$  Grade 2 infusion-related reaction, subsequent infusions may be administered at 50% of the initial rate.

Acetaminophen and/or an antihistamine (eg, diphenhydramine) or equivalent medications per institutional standard may be administered at the discretion of the Investigator. If the infusion-related reaction is  $\geq$  Grade 3 in severity, IP will be discontinued.

As with any antibody, allergic reactions to dose administration are possible. Appropriate drugs and medical equipment to treat acute anaphylactic reactions must be immediately available, and study personnel must be trained to recognize and treat anaphylaxis. The study site must have immediate access to emergency resuscitation teams and equipment in addition to the ability to admit subjects to an intensive care unit if necessary.

### 7.2.1.4. Missing Doses

Subjects will receive subcutaneous azacitidine 75 mg/m^2/day for 7 days every 28 days until the end of the study, unless they are discontinued from the treatment. In the event 2 or less doses are missed during the 7-day dosing period, dosing should continue so the subject receives the full 7 days of therapy. If 3 or more days are missed during the 7-day dosing period, the Investigator should contact the sponsor and a decision on dosing will be made on a case-by-case basis.

In order to optimally benefit from the azacitidine treatment, Investigators should aim to treat subjects for at least 6 cycles. However, subjects may be discontinued from the treatment per Investigator discretion, even during the first 6 cycles, for any of the reasons detailed in Section 11.1. If the dose of subcutaneous azacitidine is modified during the course of the study (Section 7.2.2.1) and benefit is demonstrated at a dose lower than 75 mg/m^2, that dose should be maintained during subsequent cycles that are given (unless toxicity develops). All subjects discontinued regardless of the reason will be followed for a period of 28 days following the date of the last dose of subcutaneous azacitidine or the date of the Treatment Discontinuation Visit (whichever date is later) for collection of AEs and will also be followed for survival until the end of the study.

## 7.2.2. Dose Modifications and Toxicity Management

### 7.2.2.1. Azacitidine

The first cycle of subcutaneous azacitidine should always be given at 100% of the dose, regardless of the subject's laboratory values (provided that the subject is allowed to enter the study based on the inclusion and exclusion criteria).

Subjects should be monitored for hematologic and renal toxicity; a delay in starting the next cycle or dose reduction as described by the guidance below may be necessary and followed at the investigator's discretion. Assessment to modify the dose should be made taking into consideration the subject's clinical condition including all adverse events (eg, bleeding or infections) and the subject's underlying disease status.

The Investigator should contact the sponsor's medical monitor for guidance on subcutaneous azacitidine dose modification, if needed.

#### **Dose Modifications due to Nonhematological Toxicity**

Following receipt of any dose of subcutaneous azacitidine, subsequent cycles may be delayed if a certain level of toxicity occurs after the previous dose. Any subject who experiences a nonhematological AE with Common Terminology Criteria for Adverse Events (CTCAE Version 4.03) toxicity Grade 3 or 4 that is an escalation from his or her status at baseline (prior to the first dose) should have subcutaneous azacitidine temporarily discontinued until the toxicity grade returns to less than Grade 3. Subcutaneous azacitidine should be permanently discontinued if nonhematological toxicity persists at Grade 3 or 4 for more than 21 days, despite the temporary interruption of subcutaneous azacitidine.

#### **Dose Modifications due to Hematological Toxicity**

Treatment with subcutaneous azacitidine is associated with anemia, neutropenia, and thrombocytopenia, particularly during the first 2 cycles. Complete blood counts should be performed as specified in Section 6.6.6.1 and as needed to monitor response and toxicity.

Recovery is defined as an increase of cell line(s) where hematological toxicity was observed of at least half of the difference of nadir and the baseline count plus the nadir count (ie, blood count at recovery  $\geq$  Nadir Count +  $(0.5 \times [\text{Baseline count} - \text{Nadir count}])$ ).

#### **Subjects without reduced baseline blood counts (ie, $\text{WBC} \geq 3.0 \times 10^9/\text{L}$ and absolute neutrophil count [ANC] $\geq 1.5 \times 10^9/\text{L}$ and platelets $\geq 75.0 \times 10^9/\text{L}$ ) prior to first treatment**

If hematological toxicity is observed following subcutaneous azacitidine treatment, the next cycle of subcutaneous azacitidine therapy should be delayed until platelet count and ANC have recovered. If recovery is achieved within 14 days, no dose adjustment is necessary. However, if recovery has not been achieved within 14 days, the dose should be reduced according to Table 4. Following dose modifications, the cycle duration should return to 28 days. The reduced dose should be maintained during subsequent cycles that are given (unless toxicity develops). A flow diagram for the determination of subcutaneous azacitidine dose adjustment in subjects without reduced baseline blood counts is provided in Appendix N2.

**Table 4: Dose Modifications for Subcutaneous Azacitidine in Hematologic Toxicity**

Nadir Counts		% Dose in the Next Cycle if recovery a is not achieved in next 14 days
ANC (<math>\times 10^9/L</math>)	Platelets (<math>\times 10^9/L</math>)	
$\leq 1.0$	$\leq 50.0$	50%
$> 1.0$	$> 50.0$	100%

ANC = absolute neutrophil count

a Recovery = counts  $\geq$  nadir count + (0.5  $\times$  [baseline count – nadir count]).

**Subjects with reduced baseline blood counts (ie, WBC  $< 3.0 \times 10^9/L$  or ANC  $< 1.5 \times 10^9/L$  or platelets  $< 75.0 \times 10^9/L$ ) prior to treatment**

Following subcutaneous azacitidine treatment, if the decrease in ANC or platelets from that prior to treatment is less than 50%, or greater than 50% but with an improvement in any cell line differentiation, the next cycle should not be delayed and no dose adjustment made.

If the decrease in ANC or platelets is greater than 50% from that prior to treatment, with no improvement in cell line differentiation, the next cycle of subcutaneous azacitidine therapy should be delayed until the platelet count and the ANC have recovered. If recovery is achieved within 14 days, no dose adjustment is necessary. However, if recovery has not been achieved within 14 days, bone marrow cellularity should be determined. If the bone marrow cellularity is  $> 50\%$ , no dose adjustments should be made. If bone marrow cellularity is  $\leq 50\%$ , treatment should be delayed and the dose reduced according to [Table 5](#).

**Table 5: Dose Modifications Based on Bone Marrow Cellularity**

Bone Marrow Cellularity	% Dose in the Next Course if recovery a is not achieved in next 14 days	
	Recovery $\leq 21$ days a	Recovery $> 21$ days a
15 – 50%	100%	50%
$< 15\%$	100%	33%

a Recovery = counts  $\geq$  nadir count + (0.5  $\times$  [baseline count – nadir count])

Following dose modifications, the cycle duration should return to 28 days. The reduced dose should be maintained during subsequent cycles that are given (unless toxicity develops). A flow diagram for the determination of subcutaneous azacitidine dose adjustment in subjects with reduced baseline blood counts is provided in [Appendix N1](#).

**Renal Dysfunction During Subcutaneous Azacitidine Therapy**

Renal abnormalities ranging from elevated serum creatinine to renal failure and death were reported rarely in subjects treated with intravenous azacitidine in combination with other chemotherapeutic agents. In addition, renal tubular acidosis, defined as a fall in serum bicarbonate to  $< 20$  mmol/L in association with an alkaline urine and hypokalemia (serum potassium  $< 3$  mmol/L) developed in 5 subjects with chronic myelogenous leukemia (CML) treated with azacitidine and etoposide. If unexplained reductions in serum bicarbonate

(< 20 mmol/L) occur, the dose should be reduced by 50% on the next cycle. Similarly, if unexplained elevations in serum creatinine or BUN to  $\geq 2$ -fold above baseline values and above ULN occur, the next cycle should be delayed until values return to normal or baseline and the dose should be reduced by 50% on the next treatment cycle. The reduced dose should be maintained during subsequent cycles that are given (unless toxicity develops).

#### 7.2.2.2. Durvalumab

Please refer to [Appendix M](#) for detailed instructions for dose modifications and toxicity management.

#### 7.2.3. Retreatment Criteria

In order to proceed to the next cycle, subjects must continue to meet entry criteria regarding renal and hepatic function (AST/SGOT or ALT/SGPT  $\leq 2.5 \times$  ULN, serum total bilirubin  $\leq 1.5 \times$  ULN, serum creatinine  $\leq 2.5 \times$  ULN).

Thus subjects will have laboratory assessments performed to evaluate organ function prior to starting each cycle (including Cycle 1). Because of the time it takes to obtain results from the central laboratory, samples should be collected early enough prior to starting the next cycle in order to allow sufficient time for review. In the event that immediate laboratory assessment is needed, local laboratory measurement is acceptable for starting the next cycle pending the outcome of the central laboratory assessment (ie, in addition to collecting the local laboratory sample, a matching sample should always be sent to the central laboratory).

The start of the next cycle will be delayed if the subject does not meet entry criteria regarding renal and hepatic function. If there is a delay of more than 42 days (6 weeks) in the start of the next cycle, the sponsor's medical monitor must be consulted. Study treatment should be discontinued if there is a delay of more than 56 days (8 weeks) in the start of the next cycle, unless, in the opinion of the Investigator and the sponsor's medical monitor, the subject is experiencing clinical benefit. Justification of the subject continuing in the study must be recorded in the source documents. Subjects assigned to the combination treatment arm will have azacitidine administered on Day 1 of each treatment cycle approximately one hour after completion of the durvalumab infusion, after resolution of any related AE immediately after durvalumab infusion, if any.

Prior to discontinuing a subject from study treatment, it is recommended that the investigator contact the sponsor's medical monitor and forward appropriate supporting documents for review and discussion. The decision to discontinue a subject remains the responsibility of the treating physician and will not be delayed or refused by the sponsor.

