21. Subjects who have had clinical evidence of central nervous system (CNS) or pulmonary leukostasis, disseminated intravascular coagulation, or CNS leukemia.
22. Presence of advanced malignant hepatic tumors.
23. Any of the following laboratory abnormalities:
  - Serum aspartate aminotransferase (AST/SGOT) or alanine aminotransferase (ALT/SGPT)  $> 2.5 \times$  upper limit of normal (ULN)
  - Serum total bilirubin  $> 1.5 \times$  ULN. Higher levels are acceptable if these can be attributed to active red blood cell precursor destruction within the bone marrow (ie, ineffective erythropoiesis). Subjects are excluded if there is evidence of autoimmune hemolytic anemia manifested as a corrected reticulocyte count of  $> 2\%$  with either a positive Coombs' test or over 50% of indirect bilirubin
  - Serum creatinine  $> 2.5 \times$  ULN.

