Hepatitis (elevated LFTs) Infliximab should not be used for management of immune-mediated hepatitis.	Any Grade	General Guidance	For Any Grade: 
 
Monitor and evaluate liver function test: AST, ALT, ALP, and TB.
 
Evaluate for alternative etiologies (e.g., viral hepatitis, disease progression, concomitant medications).
 

	Grade 1 (AST or ALT >ULN and ≤3.0×ULN and/or TB > ULN and ≤1.5×ULN)	
 
No dose modifications.
 
If it worsens, then treat as Grade 2 event.
 
	For Grade 1: 
 
Continue LFT monitoring per protocol.
 

	Grade 2 (AST or ALT >3.0×ULN and ≤5.0×ULN and/or TB >1.5×ULN and ≤3.0×ULN)	
 
Hold IP/study regimen dose until Grade 2 resolution to Grade ≤1.
 
If toxicity worsens, then treat as Grade 3 or Grade 4.
 
If toxicity improves to Grade ≤1 or baseline, resume IP/study regimen after completion of steroid taper.
 
	For Grade 2: 
 
Regular and frequent checking of LFTs (e.g., every 1 to 2 days) until elevations of these are improving or resolved.
 
If no resolution to Grade ≤1 in 1 to 2 days, consider, as necessary, discussing with study physician.
 
If event is persistent (>3 to 5 days) or worsens, promptly start prednisone 1 to 2 mg/kg/day PO or IV equivalent.
 
If still no improvement within 3 to 5 days despite 1 to 2 mg/kg/day of prednisone PO or IV equivalent, consider additional work up and start prompt treatment with IV methylprednisolone 2 to 4 mg/kg/day.
 
If still no improvement within 3 to 5 days despite 2 to 4 mg/kg/day of IV methylprednisolone, promptly start immunosuppressives (i.e., mycophenolate mofetil).a Discuss with study physician if mycophenolate mofetil is not available. Infliximab should NOT be used.
 
Once the subject is improving, gradually taper steroids over ≥28 days and consider prophylactic antibiotics, antifungals, and anti-PJP treatment (refer to current NCCN guidelines for treatment of cancer-related infections [Category 2B recommendation]).a
 

**PLEASE SEE shaded area immediately below this section to find guidance for management of “Hepatitis (elevated LFTS)” in HCC patients**

Specific Immune-Mediated Reactions			

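### Section 7.2.3 restates the entry bilirubin limit for retreatment but leaves out the ineffective-erythropoiesis exception in exclusion criterion 23, so a site applying the printed number could delay a validly enrolled subject

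*Protocol*

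**What the plan says.** Exclusion criterion 23 (Protocol Section 4.2.2, both cohorts) excludes total bilirubin above 1.5 × ULN, then qualifies this: "Higher levels are acceptable if these can be attributed to active red blood cell precursor destruction within the bone marrow". It sets no upper cap on the accepted value, but it still excludes subjects with evidence of autoimmune hemolytic anemia.

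Section 7.2.3 governs each further cycle: "In order to proceed to the next cycle, subjects must continue to meet entry criteria regarding renal and hepatic function". The parenthesis that follows lists AST or ALT at most 2.5 × ULN, total bilirubin at most 1.5 × ULN and creatinine at most 2.5 × ULN, with no qualification on bilirubin. The consequence is stated as "The start of the next cycle will be delayed if the subject does not meet entry criteria regarding renal and hepatic function". A delay of more than 42 days requires consultation with the medical monitor. Beyond that, "Study treatment should be discontinued if there is a delay of more than 56 days (8 weeks) in the start of the next cycle", unless the Investigator and the monitor judge that the subject is benefiting. Under Section 3.2.2, durvalumab in Arm A is delayed whenever azacitidine is.

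**The concern.** The parenthesis presents itself as a restatement of the entry rule, but it drops the qualification from the one item that has one. For a subject enrolled under the exception whose bilirubin stays high, the rule as named (the entry criteria) and the rule as printed (1.5 × ULN) give opposite dosing decisions.

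If a site follows the printed number, treatment is withheld for a disease-related value accepted at entry, although Section 7.2.5 recommends at least six cycles because response may come late. If the hold ends in discontinuation without a response, the subject counts as a non-responder in the ITT analysis (Sections 9.6.1.1.1 and 9.6.1.1.2). Without death or progression, the subject also falls outside the efficacy evaluable population (SAP Section 5.2.2). A subject who stops before the first post-baseline assessment, and without progression or a qualifying death, is replaced as well (Section 3.2.2.3).

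**Working it through.** No sample size, power or error rate is involved, so the check is a comparison of the texts plus one date calculation.

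**Item by item, exclusion criterion 23 against Section 7.2.3**

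| Item | Entry (excluded if) | Retreatment (must be) | Match? |
|---|---|---|---|
| AST or ALT | > 2.5 × ULN | ≤ 2.5 × ULN | yes |
| Creatinine | > 2.5 × ULN | ≤ 2.5 × ULN | yes |
| Total bilirubin | > 1.5 × ULN, unless due to ineffective erythropoiesis | ≤ 1.5 × ULN | cut-point yes, exception missing |

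**One subject under the two readings.** Assume bilirubin of 2.0 × ULN due to ineffective erythropoiesis (an illustrative value, not from the documents).
- Exclusion criterion 23: eligible.
- Section 7.2.3, with the entry criteria read in full: the next cycle proceeds.
- Section 7.2.3, with the printed number: the next cycle is delayed, at every cycle from Cycle 2 while the value stays above 1.5 × ULN.

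**Which reading fits the rest of Section 7.2.3.** The section goes on: "Thus subjects will have laboratory assessments performed to evaluate organ function prior to starting each cycle (including Cycle 1"). Applied there, the bare number would bar the excepted subject from the first dose and empty the exception of effect. Section 7.2.2.1 does not remove this difficulty. Its instruction to give the full first dose whatever the laboratory values is itself conditional: "provided that the subject is allowed to enter the study based on the inclusion and exclusion criteria". The reading that imports the exception is therefore the coherent one.

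**Whether another section restores the exception for retreatment.**
- Section 7.2.2.1, raised creatinine or BUN: "the next cycle should be delayed until values return to normal or baseline".
- Appendix M, Grade 2 hepatitis: "If toxicity improves to Grade ≤1 or baseline, resume IP/study regimen after completion of steroid taper".
- Appendix M, non-immune reactions: no dose modification is needed for events due to the underlying disease.

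These provisions allow for the subject's own baseline or disease. They govern toxicity management, however, and do not amend the Section 7.2.3 requirement.

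**Timing of a hold at Cycle 2 (28-day cycles).** The planned start is Day 29. Monitor consultation is required after Day 29 + 42 = Day 71, and the stopping rule applies after Day 29 + 56 = Day 85. The first post-baseline assessment follows Cycle 3, so the replacement rule can apply to a subject stopped after a hold at Cycle 2 or 3, but not at Cycle 4 or later. These dates describe any hold from any cause; they do not measure how often this omission would produce one.

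**The case against.** The strongest reply is that there is only one rule. Both operative sentences of Section 7.2.3 test the entry criteria, and the parenthesis is shorthand for them. A subject accepted under criterion 23 still meets those criteria, and the literal reading defeats itself at Cycle 1. The medical monitor also reviews eligibility before randomization (Section 3.2.1), so the sponsor can know who entered under the exception. Harm needs a chain: persistent elevation, a site that adopts the weaker reading, a hold of more than 56 days despite required consultation after 42, and no finding of clinical benefit. Section 6.7.4 counts absence of progression as benefit when deciding continuation past Cycle 6, so that waiver may be broad. The discontinuation visit includes marrow and response assessment (Section 6.14), so a response reached by then could still be recorded.

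Most of this stands, and it keeps the point small. It does not remove it: the better reading has to be inferred, while the number that sites will check is printed.

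A reader might infer that the sponsor deliberately set a stricter limit for retreatment. The documents do not support this: the other two limits match entry exactly, and the section describes itself as continuing the entry criteria.

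**Conclusion.** The point holds as a minor defect: an incomplete restatement that allows two opposite dosing decisions for a subject with accepted, disease-related hyperbilirubinemia. The coherent reading protects that subject; the printed number does not.

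Its size cannot be given. The documents do not report how many subjects enter under the exception or how many keep an elevated value, and no figure is assumed. Discontinuation is not automatic even under the literal reading.

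A reader might go further and infer a distorted response comparison or lost power. Nothing in the documents supports that: the rule is identical in both arms, and no sample size, power or error rate depends on it. The conclusion assumes only that some site could apply the printed limit as written.

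**What to change.** Amend the bilirubin item in Section 7.2.3 to read: *serum total bilirubin ≤ 1.5 × ULN, or higher if the elevation is attributed by the Investigator to ineffective erythropoiesis as accepted under exclusion criterion 23*. State that the entry criteria govern Cycle 1. Add two safeguards: any new rise not so attributed still delays the cycle, and the Appendix M hepatitis rules take precedence in Arm A when an immune-mediated cause is suspected. The second is needed because Appendix M grades total bilirubin above 1.5 and up to 3.0 × ULN as Grade 2 and requires a hold, so the two provisions overlap.

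The cost is a short amendment and a source note of the attribution whenever the exception is used. Total and direct/indirect bilirubin (Section 6.6.6.2) and reticulocytes (Section 6.6.6.1) are already scheduled on Day 1 of each cycle. A Coombs' test is not, so one may occasionally be needed if hemolysis is suspected. Because Appendix O applies Section 7.2 to the extension phase, the clarification would serve subjects treated there too.
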